Fatigue- To minimize the most likely risk of fatigue during data collection, we selected surveys that are as short as possible. Completion of the self-report survey packet requires less than one hour. Testing will be scheduled at a time that is convenient for subjects. If participants are too fatigued to complete all measures, sociodemographic and clinical data will be administered at enrollment and the baseline surveys will be gathered in a subsequent telephone call (but before randomization). All delayed data collection will occur within a two-week interval. The RAs will be trained to be sensitive to signals from participants that a break is needed during testing. All participants will be informed that they can stop their participation in the study at any time. For subjects who find data collection too fatiguing, we will offer the option of providing only the most essential data reflecting the key outcome variables (e.g., health self-care neglect).

Stress- To minimize the risk of stress during data collection the RAs will be trained to be supportive and helpful to participants with questions about data collection. If a participant becomes stressed during data collection because of the questions asked, the burden of data collection, or for other personal reasons, data collection will be terminated, delayed, or abbreviated to only the most essential items (e.g. primary outcome variable). Significant stress will be reported to the Project Manager who will contact the caregiver to discuss the issue if indicated (the PI is blinded). The RAs will be trained to detect any signals that the participant is becoming upset before stress escalates. In a prior study, we hired nursing and psychology students as RAs, which facilitated the assessment and management of participant stress during data collection. RAs will be required to have sufficient maturity and background to interact appropriately with ill, aging, stressed individuals. The protocol for the training of RAs, detailed in our operations manual, addresses enrollment methods and the collection of data in a uniform manner. Training for RAs in data collection will occur during a two-day period prior to beginning subject enrollment. Training will begin with classroom instruction, including the purpose and background on each measure, importance of strict adherence to the standardized protocol, step-by-step instruction for survey administration, criteria for aborting testing and the procedure for audiotaping sessions and transmitting data. RAs will be trained to ensure that they do not prompt subjects with verbal or nonverbal cues. Training will include practice administering all tests. Consistency in data collection procedures will be assessed and reinforced during routine staff meetings. Retraining and retesting will be done immediately if a new RA is hired and annually thereafter. The PI and the Project Manager will meet weekly or bi-weekly with staff (in-person or by video) to discuss issues of enrollment and data collection. All decisions will be logged and filed for future reference. All issues will be reported immediately to the IRB and the Data Safety Monitoring Board, as discussed in that plan.

We will be enrolling a sample of stressed individuals and it is possible that we will identify someone with severe distress. [name] (PI) has previously tested a detailed safety plan, which has been refined for use in this study. This safety plan addresses the concerns associated with severe stress that need to be handled in order to ensure that the research participants needs are addressed. This plan includes the requirement that research staff undergo training in this safety protocol and participate in ongoing regular supervision by [name] (Co-I) on these procedures. In addition, for participants randomized to the ViCCY group, specific rules to ensure privacy and safety will be discussed in the first session, such as being in a private place during sessions and not engaging in discussions while driving.

2. Benefits:

We cannot guarantee that any participant will benefit by participating in this study, although all of the caregivers will receive health information. We acknowledge that subject burden may be an issue for these already-burdened caregivers. However, we believe that the benefits of the knowledge gained will outweigh the burden and the risks to participants. A Data and Safety Monitoring Board will be used to ensure the validity and integrity of the data. We anticipate that the results of this study will benefit society most, by helping to improve the support provided to caregivers of bvFTD patients.

3. Subject Privacy:

Data will be compiled from all of the subjects in the study and aggregated for analysis and publication. All identifying data will be eliminated from files before data are electronically transferred to the biostatistician. As a result of aggregation, no individual subjects will be identifiable from the written materials. Audiotaped interviews will be assigned a unique identifier; any identifiable information in the interviews will be deleted during the transcription process. All videoconferencing sessions will be conducted using secure encrypted platforms. All companies providing third-party platforms used for this study completed the Vendor Security Technical Assessment of Risk (V-STAR) forms and have been vetted by SONs IT Department. And tablets provided to caregivers can only be used for the study.

4. Subject Confidentiality:

A trained research assistant will review the electronic medical record to make sure that the caregivers approached qualify to be participants before we invite them to join the study (eg. the patient has bvFTD). Accessing the EMR means that we will see PHI but we will limit our review to only those elements essential to establish eligibility. If the record review indicates that a caregiver is not eligible, we will note this on our paper-and-pencil log so that we do not need to repeat the review the next time the patient comes into the clinic. That paper log will be transported back to the School of Nursing and locked in a drawer until the next scheduled day of enrollment. We will not disclose the information on the log to anyone not directly involved in the study.

To protect against any risk to subject confidentiality, all printed data forms will be coded with unique identifiers. The unique identification number will be kept separate from the files with protected health information (PHI) to protect subject confidentiality. Every effort will be made to prevent anyone who is not on the research team from knowing what information was collected from a particular subject. As part of the consent process, subjects will be made aware of the fact that there are some circumstances where the research team may have to provide subject information to other people (regulatory or legal circumstances). In addition, as we are unable to ensure total Internet security, this limitation of privacy will be noted in the informed consent. In this manner caregivers will be informed that although it is highly unlikely that anyone would access an audiotaped session, the prevention of such intrusions cannot be guaranteed. The content of the intervention sessions is not anticipated to be confidential in nature.

Since this data storage system is behind multiple firewalls, is monitored regularly, and is accessible only to key personnel who receive private network/firewall, server/password, and data directory access rights, the risk of unlawful penetration is not a significant data safeguard concern. Individually identifiable or deducible data will not be transmitted by unsecured telecommunications, which include the Internet, email, and electronic File Transfer Protocol (FTP). Further, the data will not be physically moved or transmitted in any way from the server without written approval from the project manager. All output containing individual identifiable information is treated as confidential data. This information is never transferred electronically via email or other protocols.

All data will be backed up daily and system backups will be done weekly. Batch validity checks will be run on the database at periodic intervals to identify data that violate predefined rules. Data will be de-identified and stored on the database server with strong access controls, software firewall, secure file transfer protocols, network-wide virus protection software, and daily back-ups. The computers will be password-protected and maintained in a secure, locked location at the School of Nursing. Interim checks will be conducted regularly to ensure that data collection and archiving procedures are operating correctly and security and confidentiality are not compromised. All information obtained on paper (e.g., consent forms) will be numerically coded and locked in a secure location, as described further below.

Signed consent forms and other subject-specific information containing names will be kept separate from the subject identification numbers. The master list and subject information will be stored in different locked file cabinets in the PIs research offices at the University of Pennsylvania, School of Nursing. Access to these master files will be limited to those directly involved in the study.

Regarding internet access and video-conferencing sessions, study tablet devices, which are versatile for allowing privacy, will be provided to all participants and can only be used for the study. Health coaching sessions will be provided through the tablets via Secure VidyoConferencing software. Sessions are weekly initially and decrease in frequency over time. The tablet uses an embedded computer camera capable of full 2-way duplex video and audio transmissions for real-time communication. Existing broadband Internet connection is not required because we supply devices with mobile connectivity. Technology experts (Caryl Technologies, with whom we have worked in the past) will train research staff to set up Internet service.

How will confidentiality of data be maintained? Check all that apply.

Paper-based records will be kept in a secure location and only be accessible to personnel involved in the study.

- Computer-based files will only be made available to personnel involved in the study through the use of access privileges and passwords.
- Prior to access to any study-related information, personnel will be required to sign statements agreeing to protect the security and confidentiality of identifiable information.
- Whenever feasible, identifiers will be removed from study-related information.
- A Certificate of Confidentiality will be obtained, because the research could place the subject at risk of criminal or civil liability or cause damage to the subject's financial standing, employability, or liability.
- A waiver of documentation of consent is being requested, because the only link between the subject and the study would be the consent document and the primary risk is a breach of confidentiality. (This is not an option for FDA-regulated research.)
- Precautions are in place to ensure the data is secure by using passwords and encryption, because the research involves web-based surveys.
- Audio and/or video recordings will be transcribed and then destroyed to eliminate audible identification of subjects.
- Other (specify):

5. Protected Health Information

Name

Street address, city, county, precinct, zip code, and equivalent geocodes

All elements of dates (except year) for dates directly related to an individual and all ages over 89

Telephone and fax number

Electronic mail addresses

Medical record numbers

6. Compensation:

As data collection is anticipated to require significant commitment and effort on the part of subjects, remuneration will be provided. We carefully considered the amount to pay participants using the guidelines from Dickert and Grady. Because of the potential burden of data collection, we chose a market model of payment where the amount serves as an incentive rather than a reward. The advantage is more rapid recruitment and avoidance of subject financial sacrifice. Further, a completion bonus encourages subject retention. Using this model, caregivers will receive \$25 at enrollment, \$25 at 3 months and \$75 when they complete the study for a total remuneration of \$125 for a 6-month commitment. This amount is not anticipated to be undue inducement, considering the effort and commitment required of participants.

This study is funded by NIH Grant # 3R01NR018196 - 02W1.

7. Data and Safety Monitoring:

We will use a Data Monitoring Committee as described in the attached document.

8. Investigator's Risk/Benefit Assessment:

It is our judgment that benefits outweigh the risk to study participants.

INFORMED CONSENT:

1. Consent Process:

After approval by the Institutional Review Board (IRB) at Penn, the research staff will work with clinical staff to identify eligible caregivers for referral to us. To obtain a consecutive sample we will seek a HIPAA waiver to screen the clinics daily appointment schedule to identify every patient with a confirmed diagnosis of bvFTD and a potentially eligible caregiver. If enrollment from the clinic is slow we will also look for bvFTD patients participating in research at the Penn Frontotemporal

Degeneration center. Once identified, clinic or research staff will ask potential caregiver participants (e.g., those who speak English) and determine their willingness to speak with research staff about the study. Those agreeing to speak with us will have the study carefully explained to them by the research staff. Potential participants will be fully informed regarding the interventions and the schedule of the data collection. Those willing to be screened will provide verbal consent to undergo screening to assess inclusion and exclusion criteria.

After screening, the RA will obtain written informed consent from caregivers and bvFTD patients. Those who agree to participate will be asked to read and sign the consent form with integrated HIPAA authorization information (i.e., specifics about data elements to be collected and use of the private information). The consent form will specify that some intervention sessions will be audiotaped to ensure the quality of the intervention and judge treatment fidelity. We will explain that these audiotapes will be transcribed for analysis and then destroyed. We will use SameDay transcription for our audio recordings. They are a HIPAA-compliant company that has been vetted by SON's IT Department. The RAs will answer questions and make sure that the procedures that are to be used are fully understood.

The study will provide tablet devices with wireless network access and active antivirus to all participants. The tablets will only be able to be used for the study. Caregivers in both conditions will be able to access the Internet site providing Health Information (HI) content for 6 months of the study. A data plan will be provided and is included on the tablets. Research staff will provide instruction on how to use the tablet and how to access the HI website and assist participants to access the HI site if necessary. A research diary will also be provided to aid tracking of health care resources used.

In the case that participants cannot be consented in-person, participants may be consented remotely at the PI's discretion. Screening will be done by telephone and those who are eligible to participate will be pushed an electronic link that begins with the consent form. Staff will talk through the consent in detail. If the caregiver wishes to think about the study but not commit at this time, we will contact him/her at a later date. If the caregiver immediately decides to participate, the consent can be signed electronically.

2. Waiver of Informed Consent:

No waiver requested.

RESOURCES NECESSARY FOR HUMAN RESEARCH PROTECTION:

OVERALL STRUCTURE OF THE STUDY TEAM

This is a single site clinical trial with a Clinical Coordinating Center (CCC) with direct oversight by [name] and [name] and a Data Coordinating Center (DCC) with oversight by Co-Investigator [name]. Enrollment will take place primarily at the Penn Frontotemporal Degeneration Center. Oversight of the clinical intervention will be done by [name] and [name].

The Project Manager will identify training requirements relevant to the study activities and develop a training plan and process for providing and documenting training activities. This includes developing training materials (checklists, manuals, slides, and FAQs) and implementing a process for tracking. She will oversee participant enrollment, data collection, data entry and cleaning, and analysis efforts to assure that these activities take place as planned. In addition, a clinical research coordinator will be hired to facilitate smooth and efficient data collection, help with recruitment and identification of potential subjects.

Health coaches. We will hire 2-3 experienced health coaches with excellent interpersonal communication skills, and comfort with technology. The coaches will receive two days of initial training in health coaching from [name] and her team and then completed 7 hours of online training in motivational interviewing provided by the University of Colorado, College of Nursing. [name] will also provide the coaches with a day of training related to FTD and they will receive the book, "What if it's Not Alzheimer's," developed for FTD families, which contains a chapter written by [name] on common behavioral symptoms in persons with FTD. Thereafter, weekly training and supervision will be conducted by Drs. [name], [name] and [name] as the coaches begin sessions with the caregivers. As part of this supervision, audio-recordings of coaching sessions will be reviewed by independent raters using the Behavior Change Technique taxonomy. Two trained raters have judged randomly selected session recordings for each coach, assessing completeness and thoroughness of the therapeutic techniques used. We will continue to assess the quality of the coaching as we add this group of caregivers with unique issues.

Internet Access. We will leverage the current technology infrastructure from R01NR01819. We will provide tablet devices to all participating caregivers. Tablets are versatile, allowing privacy for coaching sessions and website access to those in the HI group. The tablet uses an embedded computer camera capable of full 2-way duplex video and audio transmissions for real-time communication. Existing broadband Internet connection is not required because we supply devices with mobile connectivity. Technology experts (Caryl Technologies, with whom the team currently work) will train research staff to set up

Internet service and devices with Caregivers during a virtual visit. Caregivers will be left with a step-by-step manual and the research assistant phone number in case technology issues occur.

Data Coordinating Center - Data coordination for the trial will be done by the BECCA (Biostatistics * Evaluation * Collaboration * Consultation * Analysis) Lab in the School of Nursing. The BECCA Lab is comprised of a team of highly skilled doctoral and masters level statisticians, along with Penn Nursing research assistants and biostatistics graduate interns who oversee data management and analytic activities. The lead statistician and Co-Investigator, [name] will ensure statistical rigor and appropriateness of all analyses.

Research Technology staff will develop and maintain a REDCap data management system. They will collaborate with the investigators to identify relevant clinical data from electronic medical record data (EMR) in the Penn Data Store and design, test and implement a process to import data at a scheduled frequency to data tables, which will be part of the research database. Research Technology staff will also develop programs to identify new hospital encounters for study participants using EMR information in order to initiate communication to the research staff that follow up action may be required.

Data Management staff will develop the case report forms and modify standard or template questionnaires as needed. They will design and develop the trial database and required modules. All research data for the trial will be stored in an electronic database that is managed by BECCA Lab. The database will be hosted on secure School of Nursing computing servers with access restricted to only those individuals who are authorized to work on the trial. Individual user accounts with passwords will be used to restrict access to the database. Specific privilege assignments within the database will be employed to limit the types of functions that authorized users can perform to those functions that are appropriate for their role in the trial. Additional measures to prevent unauthorized external access to the database environment will be employed using network firewall technologies.

BECCA Lab personnel will work closely with [name], [name], and the Project Manager to design, develop, and test an appropriate database structure to support the requirements of the study to promote data security and integrity. Electronic audit trails of changes to database contents are incorporated into the design and will capture and record those changes automatically. BECCA Lab personnel will configure a module to allow remote data entry from the enrollment sites. The module will be available to any computer with a persistent internet connection and will be run using standard web browser software. The data entry screens will look like the existing or reconfigured data collection forms and will allow for direct source-to database data entry, eliminating the need for paper Case Report Forms (CRFs). Data entry checks will be included in the entry screen designs where appropriate to limit the opportunity for erroneous entries due to mistyping. Such data entry checks would include value range comparisons, valid data type checks, required value checks, and skip pattern enforcement. This data entry module will be configured for single data entry.

BECCA Lab personnel will configure a module to assess data entered into the database in relation to a set of rules that describe expectations for those data items. This set of data validation rules will be defined by clinical data management personnel, working closely with [name] and the Project Manager, to identify data items that may have been collected incorrectly or entered into the database inaccurately. The module will inspect all newly entered or modified data. Clinical data management staff will review the results of the data validation and contact research staff to request corrective action for invalid data. All changes made will be recorded in an electronic audit trail and documented using change control procedures. Prior to deployment and use in the trial, the database will be subjected to extensive functional testing. Testing will include an evaluation by representative users.

Trial Close-Out: Once all data have been collected, BECCA Lab staff will lock the database. Trial data will be packaged for data sharing purposes. A snapshot of the database will be taken and stored in a secure folder.

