Fully eligible caregivers who provide informed consent will complete the baseline assessment before being randomized to study arm. The Project Manager will open a numbered sealed envelope, prepared by the team in advance, which assigns caregivers to their study arm. The Project Manager will then notify the study staff and participants of their group assignment (ViCCY or HI only) by telephone, email or message. The Project Manager will notify the study staff and participants of their group assignment (ViCCY or HI only) by telephone, email or message, as preferred by the individual. Although balance in sample size can be achieved with block randomization, the groups may not be fully comparable on other factors. Initial comparison of the groups will allow us to control for important covariates in the analyses. Investigators and all staff involved in collecting assessment data will be blinded to group assignment until after the data are locked. The Health Coaches providing the intervention and the caregiver participants will not be blinded. All baseline data will be collected prior to randomizing. Timing of follow-up assessments will be based on day of randomization

4. Administration of Surveys and/or Process:

We will enroll 30 informal bvFTD caregivers and the bvFTD patients for whom they care. After collecting baseline data, we will block randomize the caregivers 1:1 to the intervention or control group, stratifying randomization by caregiver sex and relationship to the patient (e.g., spouse, adult child) factors known to influence caregiving burden, perceived stress, and receptivity to the intervention.

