We will use a RCT design to achieve robust and unbiased results, as detailed below. We will enroll 30 informal bvFTD caregivers and the bvFTD patients for whom they care. After collecting baseline data, we will block randomize the caregivers 1:1 to the intervention or control group, stratifying randomization by caregiver sex and relationship to the patient (e.g., spouse, adult child) factors known to influence caregiving burden, perceived stress, and receptivity to the intervention. We will provide tablet devices with wireless network access and connect caregivers in both conditions to the Internet so they can access the Internet site providing Health Information (HI) content, which will be the only content provided to caregivers in the control group. In addition to HI, the intervention group will receive 10 front-loaded sessions of ViCCY over 6 months. To safeguard confidentiality, tablets provided to caregivers can only be used for the study. Assessments of self-care, perceived

stress, coping, and health status will be conducted at baseline (after enrollment but prior to randomization) and by phone at 3 and 6 months. Using contrasts within a mixed-effect modeling framework, we will assess intervention efficacy at 6 months using intention-to-treat analysis. We chose to provide 10 health coaching sessions based on our pilot data and literature demonstrating that a shorter duration of health coaching is not routinely effective. We chose to assess the primary aim at 6 months based on prior psychosocial intervention studies, but we will assess outcomes at 3-months based on this rationale: baseline (enrollment), to generate consistent profiles of all enrollees at a consistent point in time and prior to implementation of the new intervention; at 3-months, very early effects, at 6-months longer-term effects of ViCCY. We will pull resource use data from the electronic medical record (EMR) in 30-day increments and validated these data during routine follow-up calls with caregivers. We expect the proposed study to require 5 years for completion.

2. Data Collection:

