To assess changes in each of the primary and secondary outcomes over time, separate mixed effects regression models will be generated with SAS Proc Mixed. We are not powered for secondary outcomes (e.g., stress, coping, health status), but we will examine effect sizes and confidence intervals (CIs) to determine if lack of power is driving nonsignificant results. Mixed models can account for correlation between repeated measures and handle non-excessive MAR or MCAR data better than traditional models and allow for use of time-independent and time-dependent covariates. Both random slopes and random intercepts will be modeled to represent deviations from the average, or fixed-effect, slope over time and intercept, respectively. REML will be used for parameter estimation and the most appropriate covariance structure will be examined. Scores will be analyzed as repeated observations, with mean-centered baseline outcome scores serving as a covariate. Other predictor variables will include group, assessment time, and the interaction of group time (primary effect of interest). Baseline measures and group will be analyzed as time-independent covariates. The evaluation of differences in outcome profiles over time according to group will rely on the group x time interaction terms, while differences by the balancing

variables will rely on the mixed-effects modeling of higher order interaction terms. Statistical significance for individual intervention contrasts will be evaluated for each outcome, applying the Benjamini & Hochberg method to control for the type I error rate at 5%. The Akaike information criterion (AIC) will be used to evaluate overall model fit and to select the best-fitting longitudinal change pattern. We expect the groups to be balanced on baseline characteristics due to randomization; however, imbalances that occur by chance will be adjusted for in all analyses. To evaluate patient outcomes (Aim 2) over time we will use mixed effects regression modeling. As described above, scores will be analyzed as repeated observations, with mean-centered baseline outcome scores serving as a covariate. Other predictor variables will include time-dependent caregiver variables, assessment time, and the corresponding two-way interaction term (primary effect of interest).

RISK/BENEFIT ASSESSMENT:

1. Risks:

Protection Against Risk:

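### Randomisation is stratified by caregiver sex and relationship, but the Aim 1 model does not list them; if they are prognostic beyond baseline, the 6-month contrast's reported SE is too large

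*Combined protocol and SAP*

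**What the plan says.** The design is stated twice in the combined protocol and SAP, under METHODS, 4. Administration of Surveys and/or Process and under STUDY PROCEDURES, 1. Detailed Description: "we will block randomize the caregivers 1:1 to the intervention or control group, stratifying randomization by caregiver sex and relationship to the patient". Three reasons are given for the choice of factors, namely burden, stress and receptivity to the intervention: "stratifying randomization by caregiver sex and relationship to the patient (e.g., spouse, adult child) factors known to influence caregiving burden, perceived stress, and receptivity". Burden and stress are secondary outcomes H1e and H1b.

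The model is in STUDY PROCEDURES, 5. Statistical Analysis:

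- Baseline: "Scores will be analyzed as repeated observations, with mean-centered baseline outcome scores serving as a covariate".
- Remaining terms: "Other predictor variables will include group, assessment time, and the interaction of group time (primary effect of interest").
- Group comparison: "The evaluation of differences in outcome profiles over time according to group will rely on the group x time interaction terms".
- Stratifiers: they appear only where differences by the balancing "variables will rely on the mixed-effects modeling of higher order interaction terms".
- Other covariates: "imbalances that occur by chance will be adjusted for in all analyses".
- Secondary outcomes, which are not powered: "we will examine effect sizes and confidence intervals (CIs) to determine if lack of power is driving nonsignificant results".

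METHODS, 6. Subject Follow-up and the Detailed Description both say that efficacy is judged by a mixed-model contrast at 6 months, and the Aim 1 hypotheses are worded for that time point.

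**The concern.** Stratified randomisation removes most between-stratum variation from the difference between arms. A model without the strata leaves that variation in the residual, so it reports more uncertainty than the estimator has. The interaction models serve the third reason for stratifying, receptivity. For the other two, the plan does not say whether the model behind the 6-month contrast contains the main effects.

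The imbalance rule does not settle this. It has no stated test or threshold, and it looks for the very imbalance that stratification prevents.

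At stake is an avoidably wide interval in a 30-caregiver trial. This matters most for the secondary outcomes, because the plan will use their intervals to judge whether lack of power explains a null result.

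**Working it through.** **The plan's own figure.** Target Population and Accrual states over 90% power with 15 per arm for differences in longitudinal profiles on the Self-Care Inventory. No effect size, SD or within-person correlation is given, so this cannot be reproduced. A simple two-sided 5% comparison would need d = (1.960 + 1.282) × √(2/15) = 1.18 (1.23 with the t distribution).

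**Inputs.** From the documents: N = 30, 1:1, two stratifiers, baseline score as covariate, follow-up at 3 and 6 months. Assumed, because the documents give none: 60% female, 75% spouses, blocks of 4, strata explaining R² of the 6-month variance, baseline correlation ρ = 0.5, and a fraction k of the strata effect already present in the baseline score.

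**Formula.** With unit-variance scores, the residual variance after baseline is 1 − ρ². The strata part left in it is (1 − ρk)²R². Its share is s = (1 − ρk)²R² / (1 − ρ²). With perfect balance within strata, reported SE / true SD = 1/√(1 − s). At R² = 0.20:

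- k = 0: s = 0.20/0.75 = 0.267, ratio 1.168
- k = 0.5: s = 0.5625 × 0.20/0.75 = 0.150, ratio 1.085
- k = 1: s = 0.25 × 0.20/0.75 = 0.067, ratio 1.035

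At N = 30, incomplete blocks leave some imbalance, so the simulated excess is smaller. Simulated 6-month contrast at R² = 0.20, ρ = 0.5 (10,000 trials per setting; the SE/SD ranges also span a separate simulation):

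| Baseline carries strata effect | SE/SD, factors omitted | Type I error | Interval width, omitted / included | Power at 1.0 SD, omitted vs included |
|---|---|---|---|---|
| none | 1.11–1.12 | 2.8–3.0% | 1.16 | 87.6 vs 93.6 |
| half | 1.03–1.08 | 3.4% | 1.08 | 85.9 vs 89.3 |
| all | 1.01–1.02 | 4.7% | 1.03 | 85.5 vs 87.2 |

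At R² = 10% and 30% the SE excess is 6% and 20% with no carry, and 0% and 3% with full carry. With the factors included, SE/SD is 0.98 to 1.01. The true sampling SD barely changes: 0.287 omitted vs 0.277 included with no carry, 0.313 vs 0.310 with full carry.

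**Check in a mixed model.** A random-intercept model was fitted to the 3- and 6-month scores, with 80% spouses and R² = 0.2 defined beyond baseline. In blocks of 4 the mean reported SE is 0.373 omitted and 0.335 included: 0.373/0.335 = 1.113, against 1/√0.8 = 1.118. SE/SD with the factors omitted is 1.09 in blocks of 4 and 1.10 in blocks of 2. With unstructured covariance it is 1.11 and 1.13. Without stratification it is 1.00, so the excess comes from stratifying and then omitting the factors.

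**Group-by-time.** With complete data and a factor effect equal at both visits, the estimate and SE are identical with and without the main effects. With 20% of 6-month scores missing completely at random, the SE ratio is 1.000 to 1.010. If the factor effect is absent at month 3 and explains 20% at month 6, the group-by-time SE/SD is 1.06 to 1.12 across three simulations. Main effects alone do not cure that.

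**Imbalance rule.** An assumed p < 0.05 check selected a stratifier in 0 of 10,000 simulated checks at each block size (2, 4 and 6). An assumed standardised difference above 0.25 selected one in 4%, 11% and 19%.

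**The case against.** The strongest reply is that the plan is silent on the main effects and does not exclude them. A conventional interaction model contains them, and Method for Assigning Subjects to Groups leaves room to control for important covariates. That stands: a reader might infer that the plan rules the stratifiers out, and the text does not say so. But nothing makes the interaction model the one that yields the efficacy contrast.

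Second, the term that the plan calls primary is group-by-time, and power is stated for profiles over time. A reader might infer that the primary test is compromised. With complete data and a time-constant factor effect it is not.

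Third, if the factors influence burden and stress, the baseline scores should already reflect that, so the no-carry row fits the protocol's own rationale poorly. This also stands, and it points to the low end of the range. With full carry at R² = 10%, the power gain (85.2 to 85.5) is smaller than the 1.1 points lost if the factors are not prognostic.

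Fourth, the covariance model is not settled. With baseline only as a covariate, two visits give three covariance moments, while random intercept, slope, their covariance and a residual are four parameters. If baseline were instead kept as an outcome and the contrast were change from baseline, the point would largely fall away. The plan states baseline as a covariate, and for that form the random-intercept, unstructured and 6-month ANCOVA analyses agree in direction.

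**Conclusion.** The point holds in a limited form. The Aim 1 model does not list the stratifiers, and the imbalance rule will usually not add them. If they predict the 6-month outcome beyond baseline, the reported SE of the 6-month contrast is overstated by about 1% to 12% at an assumed R² of 20% and baseline correlation of 0.5, probably near the low end for burden and stress. Every prognostic input is assumed.

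A reader might infer an invalid test or a biased estimate. Neither follows: the error is conservative, with no bias and no excess of false positives. Nor do the documents say that sex or relationship influences the primary Self-Care Inventory, so a loss of precision there is possible but not shown. The exemption for group-by-time needs both complete data and a factor effect that is the same at 3 and 6 months; if that effect changes over time, its SE is overstated too.

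**What to change.** Add to STUDY PROCEDURES, 5. Statistical Analysis: each Aim 1 model includes caregiver sex and relationship to the patient as fixed effects, coded as in the randomisation strata, with sparse relationship levels combined into spouse versus other before unblinding. Add the interactions of both factors with assessment time if the group-by-time test is also to reflect the stratified design. Keep the group-by-stratifier interaction models as separate secondary analyses.

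The team should set its own definition of sparse in advance. With an assumed 75/20/5% split over three relationship levels, the third has 0 or 1 caregivers in 56% of simulated trials, and keeping sparse levels cost a further 0.3 to 1.1 points of power.

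The change is to wording only, since both factors must be known in order to randomise. Two two-level main effects use two of about 27 residual degrees of freedom (30 − 3) and cost about 1 point of power (0.4 to 1.2 in simulation) if the factors are not prognostic. Factor-by-time terms use further degrees of freedom; that cost was not calculated.
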